4.3 Study Enrollment Procedures

Identifying and recruiting candidates for the trial entails advertising the study to potentially-eligible participants who will then contact the study for screening and enrollment steps. We will perform outreach based on methods from our previous research. These approaches will be tailored to each of the three main venues at which we plan to recruit: (1) San Francisco General Hospital (SFGH)/SF Health Network: The study team has extensive experience working with the SFGH population. Recruitment in this venue will capitalize on an existing infrastructure for diabetes education. In addition, outreach will be performed at the Diabetes clinic and the General Internal Medicine clinic. (2) UCSF Clinics: We will identify potentially eligible participants through the CTSI recruitment services unit, which reviews electronic medical records and sends patient letters. We have successfully used this service in prior studies. (3) General outreach: This includes outreach through online ads and in local newspapers, posting flyers in public locations, and outreach to community clinicians. Our team has successfully applied these methods in a variety of studies.

Potential participants will make initial contact either by completing the web-based, Qualtrics-powered eligibility screening survey or by calling the study line. Before completing the online study screener, participants will be asked to review the study website as well as the full-study consent (available on the website). They will then complete an online consent to be screened for study eligibility.

Any participants who are screened eligible from the Qualtrics screening survey will complete a phone screen to determine initial eligibility. During this call, staff will confirm basic eligibility criteria. The study procedures, including what is involved in participating in the study, as well as the assessment

visits will be described to potential participants. The goal is to ensure they understand the commitment involved in study participation. Those who do not meet primary eligibility criteria will be told that they are not eligible to participate. Those who meet initial criteria and express continued interest in participating will complete craving EMA screening and assessment. Those who successfully complete the above steps will come in for an in-person screening and consent visit.

Study enrollment, including reasons for ineligibility at any point along the steps to enrollment or for non-participation of eligible candidates, will be tracked within our study Salesforce database.

Randomization to intervention group and maintenance phase track will be done via the Salesforce database. The randomization table will be programmed by a database manager, who is not otherwise involved in enrollment or other participant procedures. Randomization will be done via the Project Director, [name], who will not have access to the randomization table. When a participant ID number is entered into the database by study staff, a group assignment is revealed. This provides a computerized group assignment that cannot be altered by study staff and the group assigned is immediately recorded in the study database. Randomization will be done approximately 2 weeks prior to the start of classes in order to minimize post-randomization drop-out due to life circumstances that might affect participant ability to attend classes (e.g. such as job loss/change, family emergency, etc).

5. STUDY INTERVENTIONS

5.1 Interventions, Administration, and Duration

All participants will attend 12-weekly study intervention classes based on their random assignment: either Education alone (Ed) or Education+Mindfulness (Ed+MBI). Study groups will be held at the UCSF Osher Center for Integrative Medicine. Both groups will learn and follow a carbohydrate-restricted (CR) diet for T2DM, and will participate in maintenance phase activities. If assigned to Ed+MBI, they will also learn and practice mindfulness-based skills.

Maintenance phase: In the R61 phase, we will pilot test two levels of intensity of maintenance phase intervention (monthly group meetings alone or supplemented by individualized attention) to prepare them for R33 testing.

5.2 Handling of Study Interventions

Intervention content for the Ed program: All participants will receive instruction in the CR diet and basic behavioral strategies in a weekly, in-person, group sessions meeting for 1 to 1.25 hours for 12 weeks. A nutritionist or health professional with experience implementing CR diets with people with T2DM will train participants in how to follow the study diet, utilizing our study manual and curriculum materials developed by the team based on prior studies. The study diet has approximately 10% of kcal coming from carbohydrate, typically 50 grams/day or fewer, not including fiber. Participants will be encouraged to eat a normal amount of protein, typically about 80-100 grams/day (about 20-25% of calories), and the rest of their calories from fat. Foods that are encouraged include green leafy and other non-starchy vegetables, nuts, seeds, oils (especially olive oil), fish, poultry, tofu, and avocados. Other foods consistent with the diet include berries (in modest amounts), meats, eggs, and cheese. Key foods to minimize include any sugar-sweetened foods or beverages, bread, pasta, potatoes, highly processed packaged foods, and other starchy foods. We have developed extensive

materials to educate participants in practical and nutritionally sound approaches to a carbohydrate restricted diet.

Cognitive and behavioral components: All participants will receive core behavioral intervention components derived from the Diabetes Prevention Program (DPP),³⁶ which include goal-setting and self-monitoring of weight, diet, and physical activity..

Intervention content for the Mindfulness program: In addition to the diet components, participants randomized to the Ed+MBI group will receive MBI components using the Eat Right Now (ERN) platform. This will consist of two integrated components: 1) use of the ERN app at home, during the week, to learn and practice mindfulness skills for food-cravings and eating, and 2) in-person group-based discussions of how the mindful eating practices are going, trouble-shooting obstacles/pain points, and doing group exercises and reflecting on them. The Eat Right Now program provides brief videos of 2 to 6 minutes in length on mindfulness and mindful eating topics. Participants can watch the video segments for the week at the beginning of in-person sessions each week. The video segments can also be viewed on a smartphone or tablet at home in a self-paced manner. In person sessions will be led by an experienced mindfulness instructor with training in mindful eating and familiarity with a CR diet for T2DM, and will focus on discussion of how the mindful eating practices are going, trouble-shooting obstacles/pain points, and doing group exercises and reflecting on them. The Eat Right Now app also includes the audio tracks of meditation exercises are core components of our mindful eating program (e.g. body scan, mindful eating practices) that participants can access at any time – which will allow them to cultivate their mindfulness practice in the context of their daily lives. Twelve one-hour sessions addressing mindful eating will be conducted weekly for 12-weeks (monthly during maintenance), before each diet session. The key content of the mindful eating intervention components focuses on: helping people improve their relationship with food and control food cravings, using mindful eating approaches including: paying attention, noticing habit loops, understanding brain science and food/sugar addiction, disrupting emotional and stress eating, cultivating acceptance and curiosity, learning lovingkindness, detaching from thoughts, using healthy restraint, and maintaining motivation.

5.3 Concomitant Interventions

5.3.1 Allowed Interventions

Participants are allowed to continue on medications prescribed by their physicians, except for those outlined in the exclusion criteria: oral or parenteral glucocorticoid treatment; weight loss medications or supplements such as Alli or amphetamine-based drugs that are believed to effect on weight.

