1. Determine if our EMA measures of behavioral mechanisms have high response rates (> 90%) and are ready for R33 use.
2. Determine if there is preliminary evidence that the MBI intervention impacts our hypothesized mechanisms of action and that the proposed mechanisms predict improved dietary adherence.
3. Assess feasibility and acceptability of two intensities of maintenance (monthly group meetings alone or supplemented by individualized attention) to ensure they are ready for R33 testing.

R33 Specific Aims: We will randomize 120 persons with diabetes in a 1:2 ratio to the Ed (n=40) vs. Ed+MBI (n=80) arms and follow them for 12 months. After the 12-week intervention, we will observe participant for 8 weeks and then re-randomize them using an adaptive intervention design to receive further observation, light maintenance training, or intensive maintenance training, depending on level of adherence achieved during the observation period. We will address the following specific aims:

1. Test whether our proposed behavioral mechanisms (decreased eating in response to cravings or difficult emotions) predict dietary adherence.
2. Test the hypothesis that the Ed+MBI arm will have better dietary adherence than the Ed arm.
3. Compare randomized arms in the adaptive maintenance intervention design to optimize maintenance phase dosing in future trials.
4. Obtain preliminary assessment of intervention effects on clinical outcomes

Design and Outcomes

This is a two-phase study. Both phases will use a randomized, controlled trial design. After pilot testing in the first phase, the second phase will include employing an adaptive intervention design in the post-treatment phase to test optimization of the maintenance intervention (i.e. assigning maintenance intensity/dose based on how a participant is doing).

Interventions and Duration

Participants will attend 12-weekly study intervention classes based on their random assignment: either Education alone (Ed) or Education+Mindfulness (Ed+MBI). Both groups will learn and follow a CR diet, and will participate in maintenance phase activities. If assigned to Ed+MBI, they will also learn and practice mindfulness-based skills.

Sample Size and Population

Target sample size: 180 total (60 participants in the first/R61 phase, 120 in the second/R33 phase).

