4. SELECTION AND ENROLLMENT OF PARTICIPANTS

4.1 Inclusion Criteria

Participants must meet all of the inclusion criteria to participate in this study:

1. History of T2DM mellitus. If taking insulin, screening labs will include C-Peptide to rule out T1DM. The study intervention is not designed for people with Type 1 diabetes who make no insulin.
2. HbA1c > 6.5% and < 12.0% at screening. The lower limit confirms the diabetes diagnosis. Persons with a HbA1c > than 12% typically need immediate attention to the medical regimen, and we aim to have this done before entering the trial to better separate the effects of improved medical regimens from the diet intervention. Potential participants with a HbA1c > 12% can be enrolled once glucose control is improved.
3. Experience food-related cravings most days of the week and eat in response to these cravings regularly. A key hypothesis is that our mindfulness approach will reduce cravings and craving-related eating, and this is primary mechanistic outcome. Thus we need to recruit participants who experience this.
4. Aged 18 years old and older. We are not enrolling younger children as they may need an intervention that is better tailored to children.
5. Able to engage in light physical activity. We will be recommending physical activity as part of the intervention.
6. Willing and able to participate in the interventions. Must be interested in following a carbohydrate- restricted diet, willing to learn about mindful eating and behavioral strategies for following prescribed diets, have sufficient control over their food intake so that they can follow either diet, and otherwise be able and willing to participate in the intervention. Intervention content must be practiced to evaluate whether it is effective.
7. Have smartphone and are willing to use it on a regular basis for data collection (e.g. craving EMA assessment).
8. Ability to speak English. Groups will be conducted in English, and we do not have the capacity, given the resources available in this proposal, to translate all course material and conduct groups into another language. We enrolled Hispanic participants into the pilot study who were fluent in English, and expect to do this in the proposed study.

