Craving EMA: Those who pass the phone screen will be asked to complete the craving EMA screening and assessment. This step provides confirmation of food-craving and craving-related eating criterion. If this step is completed more than 4 weeks before the class start date, it will be repeated for baseline assessment prior to randomization.

In-person screening and consent visit: Those who successfully complete the above steps will come in for an in- person consent and screening visit. After completing written consent, they will complete additional screening and provide baseline data as follows:

- Demographics and background information
- Health history and medications to finalize screening for excluded substance abuse, mental health, medical conditions, or medications.
- Weight measurement and computerized tests of behavioral impulsivity and other cognitive tasks.

- Blood draw/labs to confirm eligibility: T2DM, HbA1c in range; TSH in normal range, normal liver and kidney function). If HbA1c is measured more than 4 weeks before the class start date, it will be repeated at the baseline blood draw.

All screening evaluations will be completed within 8 weeks prior to class start date.

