2. Hypoglycemia: The carbohydrate restricted diet may lead to decreases in glucose levels. In persons receiving medications such as sulfonylureas or insulin, this could increase the risk of hypoglycemia if appropriate medication adjustments are not made while the participant is transitioning into nutritional ketosis (once in nutritional ketosis, beta-hydroxybutyrate as a preferred CNS fuel offers some protection against symptomatic hypoglycemia.⁵⁶). In our pilot study, we used a medication reduction algorithm that resulted in no episodes of hypoglycemia. For the proposed study, we will use a similar algorithm.

Initial HbA1c	Initial medication reduction
6.5-7.0%	
 • Continue: Metformin, TZD • Reduce by 50%: Basal insulin • Stop: Secretagogue, prandial insulin, pre-mixed insulin, acarbose, GLP-1 ag/DPP4 inhibitor
7.1-8.0%	
 • Continue: Metformin, TZD • Reduce by 50%: Basal insulin, pre-mixed insulin, secretagogue, GLP-1 ag/DPP4 inhibitor • Stop: Acarbose, prandial insulin
8.1-12%	
 • Continue Metformin, TZD, secretagogue, basal insulin, GLP-1 ag/DPP4 inhibitor • Reduce by 50%: Pre-mixed insulin, • Stop: Acarbose, prandial insulin

TZD: thiazolidinedione; secretagogue: sulfonylureas and meglitinides; GLP-1 ag: glucagon like peptide 1 agonist; DPP-4 inhibitor: dipeptidyl peptidase 4

For the first 6 weeks of the trial, participants on non-insulin medications will be asked to check blood glucose (BG) fasting and pre-dinner. If taking insulin, participants will be asked to check BG before each injection (standard of care). BGs will be reviewed on a weekly basis by study physicians, including an endocrinologist. If the majority of BG values drop below 110, or there are other concerning BG patterns, we will reduce/stop medications in the following order:

1. Pre-mixed insulin
2. Secretagogue
3. GLP-1 ag/DPP4 inhibitor
4. Basal Insulin

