For each of these measures, our primary analysis will be comparison of changes from baseline to follow-up time points between groups (see overall analysis approach above). We will also assess changes from baseline to follow-up within each group to help assess the potential effect of each intervention arm on these measures. We will also test for preliminary evidence that each of these proposed mechanisms is associated with dietary adherence. Dietary adherence will be measured two ways: (1) proportion of blood ketone measures $\geq 0.3\text{mmol/L}$; (2) proportion of kcal from carbohydrate, using 24-hour diet recall. Each of our mechanism measures are continuous variables. We will therefore assess correlations between each of the mechanism measures and the dietary adherence measures, using linear regression. Finally, we will perform initial analysis of whether there are differences in two important clinical outcomes between intervention groups: HbA1c (to examine glycemic control) and weight. These clinical outcomes should result from our intermediate behavioral outcome of improved dietary adherence. We do not expect to have adequate sample-size in either phase of this study to address this question, but believe that preliminary assessment of these outcomes should be performed in case there are dramatic differences between groups even with limited sample size.

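### Ketone-based dietary adherence is analysed with no term for insulin use, which adds non-diet variance and can confound the mechanism-adherence regressions

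*Combined protocol and SAP*

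**What the plan says.** **Who may enter.** Section 4.1 admits people on insulin: "If taking insulin, screening labs will include C-Peptide to rule out T1DM". Section 5.3.1 adds: "Participants are allowed to continue on medications prescribed by their physicians, except for those outlined in the exclusion criteria". The exceptions it lists are glucocorticoids and weight-loss products, not insulin.

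**What happens to insulin.** Section 7.1 applies an initial medication change by HbA1c band, introduced thus: "we used a medication reduction algorithm that resulted in no episodes of hypoglycemia. For the proposed study, we will use a similar algorithm". For insulin the table amounts to:

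| Initial HbA1c | Basal | Pre-mixed | Prandial |
|---|---|---|---|
| 6.5-7.0% | halved | stopped | stopped |
| 7.1-8.0% | halved | halved | stopped |
| 8.1-12% | continued | halved | stopped |

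The top band reads "Continue Metformin, TZD, secretagogue, basal insulin, GLP-1 ag/DPP4 inhibitor" and "Stop: Acarbose, prandial insulin". Further reductions follow weekly review of home glucose, so they come after randomisation.

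**How adherence is scored.** Section 9.6: "Dietary adherence will be measured two ways: (1) proportion of blood ketone measures" at or above 0.3 mmol/L, and (2) the share of energy from carbohydrate by 24-hour recall. Arms are compared by t-tests and multiple regression, and mechanisms are related to adherence by linear regression. No covariate is named for either. Section 9.2 stratifies randomisation by BMI only. The Section 6.1 schedule shows ketone monitoring during the intervention and at 3 and 6 months, but not at baseline.

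**What is recorded.** Section 6.2.1 lists "Health history and medications to finalize screening for excluded substance abuse, mental health, medical conditions, or medications", and Section 6.2.4 lists medication changes at 3 and 6 months.

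**The concern.** Insulin suppresses ketone production. If so, two people eating the same diet can receive different adherence scores because one takes insulin. The plan makes insulin exposure differ between participants by rule, yet reads the ketone score as diet alone.

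Two analyses are exposed in different ways. The regressions of adherence on the mechanism measures (R61 Aim 2, R33 Aim 1) are observational, so a drug effect there can act both as noise and as a confounder. The comparison of Ed+MBI with Ed (R33 Aim 2) is randomised, so baseline insulin use acts there as noise and as a source of chance imbalance. The resilience outcome, the time for ketones to recover from below to above 0.2 mmol/L, rests on the same readings. With no baseline ketone reading scheduled, a stable drug-related difference between people cannot be removed by change from baseline or by a baseline ketone covariate.

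**Working it through.** **Inputs from the documents.** R61 has 30 per arm (Section 9.2). R33 has 40 and 80 (Précis). The correlation power statements are in Section 9.2. The plan gives no figure for the effect of insulin on ketones, for the share of participants on insulin, or for the SD of the ketone score.

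**Assumed inputs.** Share on insulin p = 0.15 to 0.40. Ketone score lower by d = 10 to 30 percentage points at equal diet. Between-person SD = 30 points.

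**1. Variance explained by insulin use.** R² = p(1-p)d²/SD².
- Low: 0.15 × 0.85 × 10²/30² = 0.014.
- High: 0.40 × 0.60 × 30²/30² = 0.24.

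The equivalent gain in sample size from adjusting is 1/(1-R²) - 1, that is 1% to 32%.

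**2. Randomised arm comparison.** The SD of the chance difference between arms in insulin share, multiplied by d, is d × √[p(1-p)(1/n₁+1/n₂)].
- 30:30: 10 × √(0.1275 × 2/30) = 0.9 points, up to 30 × √(0.24 × 2/30) = 3.8 points.
- 40:80: 10 × √(0.1275 × 0.0375) = 0.7 points, up to 30 × √(0.24 × 0.0375) = 2.8 points.

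The standard error of the arm difference at SD 30 is 30 × √(2/30) = 7.7 points (30:30) and 30 × √0.0375 = 5.8 points (40:80). The imbalance term is therefore 0.12 to 0.49 of a standard error in both designs (√R²), and the standard error already contains it. A simulation with 30% on insulin, a 30-point drop and a residual SD of 20 points gave a type I error of 5.0% for the unadjusted arm comparison.

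**3. Mechanism-adherence regressions: noise.** The nearest stated figures were first recomputed with power = Φ(atanh(r)√(n-3) - 1.96). N = 60 and r = .43 gives 93.5% (stated: above 80%). n = 30 and r = .53 gives 86.6% (stated: 80%). The second mismatch is a separate matter. If insulin carries a share m of ketone-score variance unrelated to the mechanism, r becomes r√(1-m):

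| m | N = 60: r, power | n = 30: r, power |
|---|---|---|
| 0 | .430, 93.5% | .530, 86.6% |
| 10% | .408, 90.5% | .503, 82.0% |
| 20% | .385, 86.5% | .474, 76.3% |
| 24% | .375, 84.5% | .462, 73.8% |

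**4. Mechanism-adherence regressions: confounding.** Suppose diet has no link with the mechanism, m = 20%, and insulin use correlates ρ with the mechanism measure (assumed). The induced correlation has size ρ√m: 0.2 × √0.2 = .089, or 0.3 × √0.2 = .134. At N = 60 the rejection rate is Φ(δ - 1.96) + Φ(-δ - 1.96) with δ = atanh(ρ√m)√57:
- ρ = 0.2: δ = 0.68, giving 10.4%.
- ρ = 0.3: δ = 1.02, giving 17.5%.

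Simulation (200,000 samples each) gives 10.6% and 17.6%, against a nominal 5%. The documents supply no value of ρ for the craving or stress measures. For resilience, some link follows from the physiology alone, because both sides of that regression are ketone readings.

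**The case against.** The strongest reply has four parts.

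- **Section 7.1 removes much of the insulin.** Prandial insulin stops in every band, pre-mixed insulin is halved or stopped, and basal insulin continues unchanged only at 8.1-12%. This stands. A reader of Section 5.3.1 alone might infer that participants simply stay on insulin and every other drug affecting ketones. Section 7.1 contradicts that, and the two sections should be reconciled. Some insulin still continues, and it varies between participants.
- **Adherence has a second measure.** Diet recall does not use ketones and is unaffected. That is correct, but it does not repair the ketone analysis, and Section 6.2.2 itself concedes that self-report has limitations.
- **The arm comparison is randomised, and Section 9.6 already mentions multiple regression and a baseline comparison.** Randomisation does prevent bias in expectation from baseline insulin use, so a claim that the arm difference is biased for that reason would be wrong. An unnamed covariate set is not a pre-specified adjustment.
- **The size is assumed.** This stands: at the low end the gain is trivial.

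Three stronger inferences are also not supported. First, other drug classes that raise ketones, such as SGLT2 inhibitors, are named nowhere in the documents. Second, one might infer that insulin users will be sorted as non-adherent in the R33 maintenance step. The Précis says only "depending on level of adherence achieved during the observation period" and does not define that level as ketone-based. Stratifying the re-randomisation by insulin would in any case come after such sorting and could not correct it. Third, one might infer that greater insulin withdrawal in one arm will inflate its ketone advantage. No document shows this. Withdrawal follows glucose, and so partly diet, which makes it something to report and not something to adjust for.

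**Conclusion.** The point holds in a limited form. The ketone score is read as diet alone although insulin exposure differs between participants by design, and no ketone analysis has a term for it. The main consequence is in the mechanism-adherence regressions, where insulin can attenuate a true relation or create a false one. In the randomised comparison the consequence is lost precision and chance imbalance only.

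Under the assumed inputs, insulin explains about 1-24% of ketone-score variance. At the top of that range the N = 60 regression at r = .43 still has more than 80% power, and only the Ed+MBI subset falls below it. All of this rests on general physiology and on assumed values for the insulin share, the effect and the SD. Ketone adherence is a secondary outcome. The primary EMA outcome and the recall measure do not use ketone readings.

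**What to change.** In Section 9.6:

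1. Pre-specify baseline insulin use (yes/no, from the screening medication record) as a covariate in every model with a ketone-based outcome, including resilience, and in every regression of ketone adherence on a mechanism measure.
2. Add one sensitivity analysis that leaves out baseline insulin users.
3. Report post-randomisation insulin changes by arm beside the ketone results, without adjusting for them.

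This needs only analysis wording and data already collected, and it alters no clinical rule. The cost is one degree of freedom per model. The covariate is an imperfect proxy: someone on prandial insulin alone is coded as a user although Section 7.1 stops that insulin at the start.
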